7.5 Early study termination

The study can be terminated at any time for any reason by Novartis. Should this be necessary, subjects should be seen as soon as possible and treated as a prematurely withdrawn subject. The investigator may be informed of additional procedures to be followed in order to ensure that adequate consideration is given to the protection of the subject's interests.

The investigator will be responsible for informing IRBs/IECs of the early termination of the trial.

8 Procedures and assessments

Table 8-1 Assessment Schedule, Part 1

Enoch		Soroo	nina													Troo	tment									\neg
Epoch		Scree																								
Study Phase			Ba	selin	ie			1	1							Trea	tment									
Visit numbers (internal use only)	1	2		3	3		101	102	103				10	04			105	106	107				108	; 		
Visit name (internal use only)	Screening	Day -2		Day	y -1		Day 1	Day 2	Day 3				Da	y 4			Day 5	Day 6	Day 7				Day	8		
Study Day(s)	-28 to -2	-2		-	1		1	2	3				4	4			5	6	7				8			
Time (post-dose)	-	-	0h	4h	8h	12h	-	-	-	0h	1h	ı 2h	3	h 4h	8h	12h	-	-	-	0h	1h	2ľ	3h	4h	8h	12h
Informed consent	Χ																									
Inclusion / Exclusion criteria	Χ	Х																								
Study drug administration							Χ	Χ	Х	Χ							X	Χ	Χ	Χ						
Subjects domiciled														Χ												
Medical history/current medical conditions	Χ																									
Demography	Х																									
Body height	Х																									
Body weight	Χ																									
Vital Signs	Χ	Х	Χ				Χ	Χ	Х	Χ							X	Χ	Χ	Χ						
Physical examination	Χ	Х																								
Hepatitis and HIV Screen	Χ																									
Alcohol Test, Drug Screen, and Cotinine Test	Х																									
ECG evaluation	Χ	Х																								
Hematology	Χ		Х														Х									

Epoch		Scree	nin	g												Treat	ment									
Study Phase	Screening		Ва	seli	ne											Treat	ment									
Visit numbers (internal use only)	1	2			3		101	102	103				10	4			105	106	107				108	3		
Visit name (internal use only)	Screening	Day -2		Da	ay -1		Day 1	Day 2	Day 3				Day	i 4			Day 5	Day 6	Day 7				Day	8		
Study Day(s)	-28 to -2	-2			-1		1	2	3				4				5	6	7				8			
Time (post-dose)	-	-	0h	4h	8h	12h	-	-	-	0h	1h	2h	3h	4h	8h	12h	-	-	-	0h	1h	2h	3h	4h	8h	12h
Blood chemistry ²	Х		Χ				Х	X	Х	Χ							Х	Х	Х	Х						
Urinalysis	X		Х				X										X									
Urine albumin:creatinine ratio ³			Х				Х										Х									
Corporate Confidential Information			Х														Х									
			Х														Х									
			Х	Х	Χ	Х	X			Χ				Х	Х	Х	X			Х				Х	Χ	Χ
				Х	Χ	Х	Х							Х	Х	Х	X							Х	Χ	Χ
										Χ	Χ	Χ	Х	Х	Х	Х	X			Х	Х	Χ	Χ	Х	Χ	Χ
							X																			
	X		Х																Х							
Columbia-Suicide Severity Rating Scale	Х	Х																								
Adverse events							·					>	(·									
Concomitant therapies												>	(
Phase/Study completion information			Х																							

Epoch									٦	Freatm	nent			
Study Phase						Trea	tment						Study Completion /Early termination	30 day Safety Follow up call
Visit numbers (internal use only)	109	110	111				112				113	114	199	n/a
Visit name (internal use only)	Day 9	Day 10	Day 11				Day 1	2			Day 13	Day 14	End of study	
Study Day(s)	9	10	11				12				13	14	21 -1 +2	51
Time (post-dose)	-	-	-	0h	1h	2h	3h	4h	8h	12h	-	-	-	
Informed consent														
Inclusion / Exclusion criteria														
Study drug administration	Χ	Х	Х	Х										
Subjects domiciled					>	(
Medical history/current medical conditions														
Demography														
Body height														
Body weight														
Vital Signs	Χ	Χ	Х	Х							Х	Х	X	
Physical examination			Х										X	
Hepatitis and HIV Screen														
Alcohol Test, Drug Screen, and Cotinine Test														
ECG evaluation													X	
Hematology	Х										Х		X	
Blood chemistry ²	Χ	Χ	Х	Х							Х	Χ	X	
Urinalysis	Χ										Х		X	
Corporate Confidential	Х										Х		X	
Information	Х										Х			
	Х										Х		X	
	Х			Х				Х	Х	Х	Х			
·	Х							Х	Х	Х	Х			
PK blood collection ⁶	Χ			Х	Х	Х	Х	Х	Х	Х	Х			

Epoch									٦	Гreatm	ent			
Study Phase						Treat	tment						Study Completion /Early termination	30 day Safety Follow up call
Visit numbers (internal use only)	109	110	111				112				113	114	199	n/a
Visit name (internal use only)	Day 9	Day 10	Day 11			ı	Day 12	2			Day 13	Day 14	End of study	
Study Day(s)	9	10	11				12				13	4.4	21	51
Study Day(s)	9	10	11				12				13	14	-1 +2	
Time (post-dose)	-	-	-	0h	1h	2h	3h	4h	8h	12h	-	-	-	
Corporate Confidential														
Information													Х	
Columbia-Suicide Severity Rating Scale											Х		X	
Adverse events										Х				X
Concomitant therapies										Х				
Phase/Study completion information			Х										X	

¹ Visit structure given for internal programming purpose only

Corporate Confidential Information

Corporate Confidential Information

² including Cystatin C

³ First morning void

 $^{^{\}rm 6}$ PK blood samples obtained at 0h will be pre-dose samples on Days 4, 8 and 12

⁷ Pre-dose

⁹ Assessments on Study Days 1-3, 5-7, and 9-11 should be done pre-dose.

Table 8-2 Assessment schedule Part 2, Patients 1-16

Epoch	Scree	ning													Treatr	nent									
Study Phase	Screening	Baseline											Т	reatme	nt									Study Completion	30 Day safety follow up call
Visit Numbers ¹	V1	V2 ²	V3	V3.1	V3.2				V3.	3			V3.4	V3.5	V4 ³	V5	V6			\	/7			V777	n/a
Visit numbers (internal use only)	1	4	201	201.1	201.2	2			201.	.3			201.4	201.5	202	203	204			2	05			299	
Visit name (internal use only)	Screening	Day -1	Day 1	Day 2	Day 3			I	Day	4			Day 5	Day 6	Day 7	Day 14	Day 21			Da	y 28			End of study	
Study Day(s)	-28 to -4	-1	1	2	3				4				5	6	7	14	21			2	28			35	65
Study Day(s)	-20 10 -4	-1													-1 +1	-1 +1	-1 +1			-1	+0			-1 +2	
Time (post-dose)	-	0h	-			0h	1h	2h	3h	4h	8h	12h			-	-	-	0h	1h	2h	3h	4h	8h	-	
Informed consent	Х																								
Inclusion / Exclusion criteria	Х	х																							
Dose administration ⁴														Х											
Domicile								Χ																	
Medical history/current medical conditions	×																								
Demography	Х																								
Body height	Х																								
Body weight	Х																								
Hepatitis and HIV Screen	Х																								
Vital Signs	Х	Х	Х	Х	Х				Χ				Х	Х	Χ	Χ	Х	Х						Х	
Physical	Χ	Х																Х						Х	

Epoch	Scree	ning													Treatr	nent									
Study Phase	Screening												Т	reatme										Study Completion	30 Day safety follow up call
Visit Numbers ¹	V1	V2 ²	V3	V3.1	V3.2			,	V3.3	3			V3.4	V3.5	V4 ³	V5	V6			\	/7			V777	n/a
Visit numbers (internal use only)	1	4	201	201.1	201.2			2	201.	3			201.4	201.5	202	203	204			2	05			299	
Visit name (internal use only)	Screening	Day -1	Day 1	Day 2	Day 3			D	ay	4			Day 5	Day 6	Day 7	Day 14	Day 21			Da	y 28			End of study	
Study Day(s)	-28 to -4	-1	1	2	3				4				5	6	7	14	21				28			35	65
			-						-						-1 +1	-1 +1	-1 +1		1		+0	ı	1	-1 +2	
Time (post-dose)	-	0h	-			0h	1h	2h	3h	4h	8h	12h			-	-	-	0h	1h	2h	3h	4h	8h	-	
examination																				 	-	ļ			
Alcohol Test, Drug Screen, and Cotinine Test	Х																								
ECG evaluation	Х																							X	
Hematology	Х	Х														Х		Х						Х	
Blood chemistry ⁵	Х	Х	Х	Х	Х				Χ				Х	Х	Х	Х	Х	Х						Х	
Urinalysis	Х	Х	Х	Х	Х				Х				Х	Х	Х	Х	Х	Х						Х	
Corporate Confidential Information	Х	Х	Х	Х	х				Х				Х	х	Х	Х	Х	Х						х	
		Х													Х			Х							
	×	Х	Х												Х	Х		x						Х	
	X	Х													Х			Х							

Epoch	Scree	ning														Treat	ment										
Study Phase	Screening	Baseline												Tr	reatme	nt										Study Completion	30 Day safety follow up call
Visit Numbers ¹	V1	V2 ²	V3	V3.1	V3.2				V3	.3				V3.4	V3.5	V4 ³	V5		V6			١	/7			V777	n/a
Visit numbers (internal use only)	1	4	201	201.1	201.2				201	1.3			2	201.4	201.5	202	203	2	204			2	05			299	
Visit name (internal use only)	Screening	Day -1	Day 1	Day 2	Day 3				Day	4				Day 5	Day 6	Day 7	Day 14		Day 21			Da	y 28			End of study	
Study Day(s)	-28 to -4	-1	1	2	3				4	ļ				5	6	7 -1 +1	14 -1 +1		21 1 +1				28 +0			35 -1 +2	65
Time (post-dose)	-	0h	-			0h	1h	2h	3h	41	n 8I	h 1:	2h			-	-		-	0h	1h	2h	3h	4h	8h	-	
PK blood collection ⁹						Х	Х	Х	Х	X	X		Х	Х		Х	Х		Х	Х	Х	Х	Х	Х	Х		
Adverse events															×												
Columbia-Suicide Severity Rating Scale	Х	Х															х			Х						X	
Concomitant Medication															Х												
Arterial spin labeling MRI ¹⁰		Х														Х											
Phase/Study completion information		Х																								Х	

¹ Visit structure given for internal programming purpose only

Information

² MRI can be done within 2 days prior to the baseline visit

³ MRI can be conducted within a day +/- of the Day 7 visit

⁴ Patient is expected to take the drug every day for 4 weeks. Corporate Confidential

Corporate Confidential Information

Table 8-3 Assessment Schedule, Part 2 Patients 17 to 72, approximately

Epoch	Scree	ning						Treatr	nent					
Study Phase	Screening	Baseline				Treat	ment						Study Completion	30 Day safety follow up call
Visit Numbers ¹	V1	V2 ²	V3	V4 ³	V5	V6			٧	7			V777	n/a
Visit numbers (internal use only)	1	4	201	202	203	204			2	05			299	
Visit name (internal use only)	Screening	Day -1	Day 1	Day 7	Day 14	Day 21			Da	y 28			End of study	
Study Day(a)	-28 to -4	4	1	7	14	21			2	8			35	65
Study Day(s)	-20 10 -4	-1	1	-1 +1	-1 +1	-1 +1			-1	+0			-1 +2	
Time (post-dose)	•	0h	•	-	-	-	0h	1h	2h	3h	4h	8h	-	
Informed consent	Х													
Inclusion / Exclusion criteria	X	Х												
Dose administration ⁴						×	(
Medical history/current medical conditions	Х													
Demography	X													
Body height	Х													
Body weight	Х													
Hepatitis and HIV Screen	Х													
Vital Signs	Х	Х	Х	Х	Х	Х	Х						Х	
Physical examination	Х	Х					Х						Х	
Alcohol Test, Drug Screen, and Cotinine Test	Х													
ECG evaluation	X												X	
Hematology	Χ	Х			Х		Х						Х	
Blood chemistry ⁵	Х	Х	Х	Х	Х	Х	Х						Х	
Urinalysis	Х	Х	Х	Х	Х	Х	Х						X	
Corporate Confidential Information	Х	Х	Х	Х	Х	Х	Х						Х	
		Х		Х			Х							
	Х	Х	Х	Х	Х		Х						Х	
	Х	Х		Х			Х							
PK blood collection ⁹				Х	Х	Х	Х	Х	Х	Х	Х	Х		
Adverse events							Х							Х

Epoch	Scree	ning						Treatr	nent					
Study Phase	Screening	Baseline				Treat	ment						Study Completion	30 Day safety follow up call
Visit Numbers ¹	V1	V2 ²	V3	V4 ³	V5	V6			٧	7			V777	n/a
Visit numbers (internal use only)	1	4	201	202	203	204			20	05			299	
Visit name (internal use only)	Screening	Day -1	Day 1	Day 7	Day 14	Day 21			Day 28				End of study	
Study Day(s)	-28 to -4	-1	1	7 -1 +1	14 -1 +1	21 -1 +1			28 -1 +0				35 -1 +2	65
Time (post-dose)	-	0h	-	-	-	-	0h	1h	2h	3h	4h	8h	-	
Columbia-Suicide Severity Rating Scale	Х	Х			Х		Х						Х	
Concomitant therapies						Х								
Arterial spin labeling MRI ¹⁰		Х		Х										
Phase/Study completion information		Х											Х	

¹ Visit structure given for internal programming purpose only
2 MRI can be done within 2 days prior to the baseline visit
3 MRI can be conducted within a day +/- of the Day 7 visit
4 Patient is expected to take the drug every day for 4 weeks
Corporate Confidential Information

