3.1 Study design

Part 1 will be enrolled as a cohort of 12 subjects (2:1 LHW090 and placebo). Patients will be domiciled from Day -2 to Day 14.

Corporate Confidential Information

Part 2 First 16 patients will be domiciled for 1 week, from day -2 to Dav 7. Rest of the dosing will be done off site.

Part 2 will enroll n=72 patients randomized 3:3:2 to LHW090 and placebo.

Corporate Confidential Information

This is a randomized, double-blind, parallel group, placebo-controlled study, in two sequential parts to evaluate the renal safety, tolerability and pharmacokinetics of LHW090 in patients with moderately impaired renal function. Patients aged 40 to 85 (inclusive) with an estimated glomerular filtration rate (eGFR) between 30 and 59 mL/min/1.73m² at screening (inclusive) on a stable dose of an angiotensin receptor blocker (ARB) will be considered for this study.

The study will be conducted in two parts. Part 1 will enroll a single cohort of 12 patients who will be randomized in a 2:1 ratio of LHW090 to placebo. An intra-patient dose escalation scheme will be employed starting at a daily dose for the first four day cycle, and then the dose will be escalated once daily for the next four days and then once daily for four days. If a renal event occurs during the treatment periods of the study or any of the individual stopping criteria are met, then dosing will be stopped for that individual patient. For the purposes of this study, a renal event will be defined as a reproducible increase from baseline serum creatinine of ≥ 0.3 mg/dL confirmed on a repeat measurement within 24-48 hours (Mehta et al 2007, Khwaja 2012). Throughout the study, any serum creatinine assessment that is increased ≥ 0.3 mg/dL compared to baseline will trigger a repeat assessment of serum creatinine after 24 hours to confirm whether criterion for a renal event is met.

function Corporate Confidential Information will be performed Starting on Day 1, the patient will begin treatment with study drug or placebo, and dose will escalate two times for a total dosing period of 12 days. Pharmacokinetic assessments will be collected as shown in the assessment schedule. After completing dosing, patients will be monitored for an additional 48 hours after which they will be discharged at the discretion of the investigator. The patient will be asked to return to the site approximately one week later for end of study assessments.

Corporate Confidential Information

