3.3 Rationale of dose/regimen, duration of treatment

In Part 1, patients will receive escalating doses of LHW090 Corporate Confidential Information with each dose administered once daily for four days.

The pharmacokinetics of LHW090 and LHV527 is anticipated to be similar between Parts 1 and 2. Likewise, after the domiciling period for Part 2, LHW090 pharmacokinetics of LHW090 and LHV527 are also anticipated to be similar at the end of Part 2 (i.e., day 28).

Page 29 Protocol No. CLHW090X2102

In Part 2, importantly, although the proposed doses of LHW090 are daily, pending evaluation of data from Part 1, a lower dose may be studied Corporate Confidential Information

once

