3.6 Risks and benefits

There is no benefit expected for subjects participating in this study. In Part 1, patients will receive escalating doses of LHW090 four days. Corporate Confidential Information

over

Based on other compounds with a similar mode of action, low blood pressure may be a potential risk.

Corporate Confidential Information

An allergic-type reaction called angioedema has been reported with a compound with a similar mode of action as LHW090. This risk may be increased when LHW090 is taken concomitantly with an ACE inhibitor. Subjects who are unable to substitute an ACE inhibitor with an angiotensin receptor blocker are excluded from this study. Due to the potential for pharmacokinetic drug-drug interactions, subjects taking statins should be monitored for statin-related myopathy during the duration of the study. For further details, refer to the Investigator Brochure and Section 5.2 "Prohibited treatment".

The risk to subjects in this trial will be minimized by adherence to the eligibility criteria, individual and study stopping criteria, and close clinical monitoring. Clinical monitoring includes regular monitoring of renal function in an in-patient setting in Part 1.

Corporate Confidential Information

In Part 1, a maximum of 235 mL of blood is planned to be collected over a period of 7 weeks from each subject as part of the study. In Part 2, a maximum of 135 mL of blood is planned to be collected over a period of 9 weeks from each subject as part of the study. Additional samples for monitoring of any safety findings would be in addition to this. This is not considered to be a risk for this population.

There may be unknown risks of LHW090 which may be serious and unforeseen.

4 Population

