Study treatment must be discontinued and the patient withdrawn from the study if the patient withdraws consent. Patients may voluntarily withdraw from the study for any reason at any time. They may be considered withdrawn if they state an intention to withdraw, fail to return for visits, or become lost to follow-up for any other reason. If a patient withdrawal occurs for any reason, the Investigator must make every effort to determine the primary reason for a patient's withdrawal from the study and record this information on the CRF.

The Investigator should discontinue study treatment for a given patient or withdraw the patient from study if on balance they believe that continuation would be detrimental to the patient's well-being. Under the following circumstances, individual study treatment must be discontinued and the patient monitored until resolution of the reason for discontinuation according to the Investigator's discretion:

- A reproducible and persistent (confirmed on repeat assessment within 24 48 hr) increase
 in serum creatinine ≥0.3 mg/dL from baseline. Any increases in serum creatinine
 ≥0.3 mg/dL based on local laboratory assessments should trigger repeat assessments of
 serum creatinine until event resolution (e.g. serum creatinine within 10% of baseline) or
 event stabilization. Baseline is defined as the average of all available pre-dose
 measurements.
- Systolic blood pressure <90 mm Hg (must be confirmed on repeat measurement after 30 minutes) or symptomatic hypotension
- Any protocol deviation (e.g. use of an ACE inhibitor) that results in a significant risk to the patient's safety

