8.4 Safety

Safety assessments are specified below; methods for assessment and recording are specified in the Site Operations Manual, with the Assessment Schedule detailing when each assessment is to be performed.

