11.4.2 Statistical model, hypothesis, and method of analysis

Part 1:

The purpose of the dose escalation in Part 1 is to assess the renal safety and tolerability of multiple doses of LHW090 in patients with moderately impaired renal function starting with the highest single dose tested in renal patients in the first-in-human study before the start of Part 2. Descriptive summary statistics will be provided by treatment group and visit/sampling time point, for change from baseline serum creatinine including the frequency (n, %) of renal events <0.3 mg/dL and ≥ 0.3 mg/dL.

Concentration response modeling may be carried out in Part 1 to assess the correlation of change in serum creatinine with concentration. In the absence of a significant concentration effect on serum creatinine, Part 2 will be initiated Corporate Confidential Information If there is evidence of significant concentration effect, Part 2 of the study may not be initiated or a lower dose may be investigated.

Part 2:

For Part 2, a Chi-square test will be performed to compare the proportion of patients who develop a renal event in the LHW090 pooled active doses, LHW090 individual doses and placebo groups. This analysis will be stratified by ARB dose (see Appendix 2). A logistic model with the baseline ARB dose and the baseline creatinine level as covariates may also be used. P-value and 95% CI of the difference in proportions will be presented. Descriptive summary statistics will be provided by treatment and visit/sampling time point, for change from baseline serum creatinine including the frequency (n, %) of renal events <0.3 mg/dL and ≥ 0.3 mg/dL will be provided.

Historical data from internal Novartis studies in a similar patient population may be used to supplement the information from patients on placebo in the current study.

Analyses stratified by degree of proteinuria (microalbuminuria or macroalbuminuria) and/or history of diabetes may also be conducted.

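### Part 1 schedules no blood pressure reading between 1 and 12 hours after any dose, although low blood pressure is a named risk and a stopping criterion

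*Protocol*

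**What the plan says.** Protocol Section 8.4 leaves the methods of safety assessments to the Site Operations Manual and their timing to the schedule, "with the Assessment Schedule detailing when each assessment is to be performed". For Part 1 the schedule is Table 8-1. Vital signs, which include blood pressure (Section 8.4.2), have their own unredacted row.

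- **Days 4, 8 and 12** are split into columns at 0, 1, 2, 3, 4, 8 and 12 h. Vital signs are marked under 0h, and the six later cells are empty. Footnote 6 fixes the meaning of 0h for PK: "PK blood samples obtained at 0h will be pre-dose samples on Days 4, 8 and 12".
- **Days 1-3, 5-7 and 9-11** have one undivided column each, with vital signs marked. Footnote 9 reads "Assessments on Study Days 1-3, 5-7, and 9-11 should be done pre-dose".
- **After the last dose**, vital signs are marked on Days 13 and 14 and at end of study.

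On risk, Section 3.6 says, from experience with similar compounds, that "low blood pressure may be a potential risk". Section 7.1 lists as a mandatory reason to stop treatment: "Systolic blood pressure <90 mm Hg (must be confirmed on repeat measurement after 30 minutes) or symptomatic hypotension".

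On dosing, Section 3.1 says the "dose will escalate two times for a total dosing period of 12 days", with four days at each level. Section 11.4.2 describes Part 1 as "starting with the highest single dose tested in renal patients in the first-in-human study". Section 3.3 adds for Part 2 that, "pending evaluation of data from Part 1, a lower dose may be studied".

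**The concern.** The plan names hypotension as a risk and sets a numerical stop for it, but it schedules no measurement in the hours after dosing, when an acute effect would be looked for. The stopping criterion has two separate limbs. Symptoms alone are enough for one. The other, a systolic value below 90 mm Hg confirmed after 30 minutes, needs a reading. A fall that comes and goes within the day without symptoms can meet that limb only if someone happens to take an unscheduled pressure.

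The patients are not at low prior risk. All take an ARB, and Section 1.1 states that neprilysin inhibition combined with an ARB lowers blood pressure. Section 4.2 admits a sitting systolic pressure of 100 mm Hg, so such a patient crosses the threshold after a fall of just over 10 mm Hg.

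Part 1 is also the setting best suited to finding this. Patients are domiciled from Day -2 to Day 14, and the results are meant to inform the design of Part 2. In Part 2 only the first 16 patients are domiciled, for about a week. As planned, the SAP Section 7.4 vital-signs tables for Part 1 would contain no rows between 1 and 12 h.

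**Working it through.** The plan gives no figure to reproduce. The check is a count of marks in Table 8-1, with each row aligned to its column headers (26 columns in the first half of the table, 14 in the second).

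| Days | Vital signs marked | Timing | Readings at 1-12 h |
|---|---|---|---|
| 1-3, 5-7, 9-11 | 9 | pre-dose (footnote 9) | 0 |
| 4, 8, 12 | 3 | 0h column | 0 |
| All 12 dosing days | 12 | | **0 of 12** |

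**First reading after each new dose level.** With four days per level, new levels start on Days 1, 5 and 9. The reading on each of those days precedes the dose, so the next is the pre-dose reading on Day 2, 6 or 10, about 24 h later. Overall, all 12 doses are followed by a reading at about 24 h (Days 2 to 13).

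**Comparison with PK sampling.** Post-dose draws at 1-12 h: 6 times × 3 days = 18. Draws at about 24 h (Days 5, 9 and 13): 3. Total 21. Blood pressure is scheduled alongside 3 of the 21, all at about 24 h, and alongside none of the 18. SAP Section 7.3 allows PK concentration to be plotted against safety measures at matching times. For blood pressure in Part 1 no pairs would exist at 1-12 h.

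**Cohort size.** Randomisation is 2:1 in 12 patients, giving 8 active and 4 placebo. If all complete dosing:

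- patient-doses: 12 × 12 = 144
- active: 8 × 12 = 96
- placebo: 4 × 12 = 48
- active doses after the first escalation (Days 5-12): 8 × 8 = 64

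Section 11.4.2 puts the starting dose at the highest single dose given to renal patients in the first-in-human study. The 64 doses on Days 5-12 are therefore above that dose.

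**Reading the table.** The marker for footnote 9 is not visible in the available text. Its wording covers assessments in general on the days without hourly columns, and on Days 2, 3, 6 and 10 vital signs and blood chemistry are the only assessments marked in the visible rows. The PK row label is lost in the first half of the table; the row is identified by its pattern and by footnote 6. Footnotes 4, 5 and 8 are not visible.

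**The case against.** **Footnote 9 may belong to blood chemistry alone.** Chemistry has marks on the same days and must be an early-morning fasting sample (Section 8.4.4). The readings on those nine days would then have no stated time, and the 24-hour gap after each new dose level would not be fixed by the plan. This stands as an uncertainty about those nine days. It does not help the plan: the schedule would still require no post-dose reading on any day, and the 1-12 h cells on Days 4, 8 and 12 are blank regardless.

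**The justification may be redacted.** Text is removed right after the sentence on low blood pressure and in the data summary and dose rationale. First-in-human data could support once-daily readings. That cannot be excluded, and it limits what can be said about size. Section 3.2 also says Part 1 was chosen to assess doses below the expected therapeutic doses, though it adds that dosing escalates to the target dose.

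**Other safeguards exist.** Patients are in-house, the investigator monitors adverse events continuously, extra checks may be made case by case (Section 13), symptomatic hypotension alone stops treatment, and a sustained fall would show at the next daily reading. All true. However, Sections 3.2 and 3.6 tie in-patient monitoring to renal function and PK, and reactive checks neither reliably detect symptom-free falls nor compare active with placebo.

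**No visible Part 2 decision rule uses blood pressure.** The only visible rule, in Section 11.4.2, concerns creatinine. This is fair: the link to Part 2 is through Part 1's general safety objective, and the primary analysis is unaffected.

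**Conclusion.** The gap is real. As the schedule reads, 0 of 12 Part 1 doses, and none of 144 planned patient-doses, have a scheduled blood pressure at 1-12 h. That includes the first dose at each new level. What goes unmeasured is a transient, symptom-free fall after dosing; symptomatic or sustained hypotension would probably be found by other routes.

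The conclusion assumes that the visible Vital Signs row is complete, that 0h for vital signs means around dosing rather than later, and that no hidden footnote adds readings. The 24-hour gap also assumes that footnote 9 covers vital signs. The frequency and depth of any missed fall cannot be estimated from the documents. The change should be made because it is cheap and bears on patient safety and on what Part 1 can tell Part 2. It does not invalidate the design. Part 2 timing and the study-hold rule for falls lasting more than 8 hours are outside this point.

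**What to change.** **Protocol, Table 8-1, Vital Signs row.** Add sitting blood pressure and pulse, taken before the blood draw, at the existing 1, 2, 3, 4, 8 and 12 h PK times on Days 4, 8 and 12. Add the same at 2, 4 and 8 h on Days 1, 5 and 9, the first day at each dose level. Add to footnote 9 an exception for the 2, 4 and 8 h vital signs on Days 1, 5 and 9.

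**SAP Section 7.4.** For Part 1, summarise vital signs by nominal post-dose time. Report by treatment the lowest post-dose systolic pressure per patient at each dose level, and the number of patients with a confirmed value below 90 mm Hg.

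**Cost.**

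- Days 4, 8 and 12: 6 × 3 = 18 readings per patient, 18 × 12 = 216 in all, at draws already planned.
- Days 1, 5 and 9: 3 × 3 = 9 per patient, 9 × 12 = 108 in all, while patients are domiciled.
- Total: 27 per patient, 216 + 108 = 324.

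No new visit or blood sample is needed, but the protocol change needs an amendment with the usual approvals.

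**Downsides.** More readings mean some chance low values, though a stop still needs confirmation after 30 minutes. Blinded staff may get a slight hint of treatment. The comparison of 8 active with 4 placebo patients is descriptive only.

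**Optional refinements.** Readings at the existing 4, 8 and 12 h columns on Day -1 would give a time-matched baseline at those times (3 × 12 = 36 more readings). Standing readings would capture orthostatic change. The concurrent placebo arm makes neither essential.
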